8.6.3.2 DNA analysis

After fully blinded genotyping has taken place, the results of the genotyping will be correlated with the salivary melatonin concentration, actigraphy results and clinical phenotype of the individuals. For the clinical phenotype outcomes, two approaches will be taken. Firstly, association with the primary outcome of the trial will be undertaken. Secondly, mutually exclusive subgroups will be defined (without reference to the genotyping results) with regard to a combination of the CSHQ, actigraphy and dim-light melatonin onset (DLMO) salivary sample results. The disorders most relevant to endogenous melatonin production will be Circadian rhythm sleep disorders (CRSD) either advanced, delayed or free-running.

8.7 Loss to Follow-up

If any of the trial patients are lost to follow up, contact will initially be attempted through the trial RP and the lead investigator at each Centre. If the lead investigator at the trial Centre is not the patient's usual clinician responsible for their speciality care then follow-up will also be attempted through this clinician. Where all of these attempts are unsuccessful, the child's GP and/or District Nurse will be asked to contact the family and provide follow-up information to the recruiting Centre. This information will be included on the patient information sheet.

8.8 Trial Closure

The end of the trial will be considered as the date of the final database lock; however the trial may be closed prematurely by the Trial Steering Committee, on the recommendation of the Data Monitoring Committee, for reasons such as clear differences between the safety of trial treatments.

9 STATISTICAL CONSIDERATIONS

9.1 Introduction

A separate and full statistical analysis plan will be developed prior to the analysis of the trial. The analysis plan will be agreed by the Trial Steering Committee before being sent to the Data Monitoring Committee for comment and approval.

9.2 Method of Randomisation

Randomisation lists will be generated in STATA using simple block randomisation with random variable block length. Randomisation will be stratified by centre.

9.3 Outcome Measures

9.3.1 Primary

1. Total night-time sleep (time from sleep onset to off-set, minus night awakenings)

Data for this outcome will be taken from the sleep diaries. The sleep diary (Section 8.3.1) covers a period of one week and parents document their child's bed time, time they fall asleep and the final time that they wake up in the morning. The diary therefore allows parental perception of their child's sleep periods to be documented. Total sleep time is calculated as the time from sleep onset to off-set minus any night awakenings.

Total night-time sleep may also be calculated from the actigraph data and this will be done as a secondary outcome to be crosschecked with the sleep diary data.

*Sleep diary records parental perception of a child's sleep. Parents are not required to differentiate between periods where the child is actually asleep and periods where the child is awake but quiet e.g. not disturbing the rest of the household. Therefore parents do not have to stay awake to complete the sleep diary.

**'Snuggle down time' is defined as 'the time you stop other activities, and ask, suggest or encourage your child to settle down for sleep. For many children this will be when they lie down (usually in bed) and the lights are turned off or dimmed.'

A minimum of 5 out of 7 nights of sleep diary data is required for analysis. Week T-1W will be used as the baseline to be compared with week T+11W.

9.3.2 Secondary

1. Total night time sleep calculated using actigraphy data
2. Sleep efficiency calculated by (number of minutes spent sleeping in bed/total number of minutes spent in bed) x 100
3. Sleep onset latency (the time taken to fall asleep) calculated using actigraphy
4. Sleep onset latency (the time taken to fall asleep) calculated using sleep diaries
5. Composite sleep disturbance index scores
6. Daily global measure of parental perception of child's sleep quality
7. Behavioural problems assessed using Aberrant Behaviour Checklist (ABC)

8. Quality of Life of the parent assessed using the Family Impact Module of the PedsQL™
9. Level of daytime sleepiness in caregivers assessed using Epworth Sleepiness Scale
10. Number and severity of seizures evaluated using seizure diaries throughout trial follow-up
11. Adverse effects of melatonin treatment assessed weekly between weeks T0W to T12W using 'TESS' (Treatment Emergent Signs and Symptoms) (Section 8.4.1)
12. Salivary melatonin concentrations
13. Associations between genetic variants and abnormal melatonin production.

*Sleep onset latency (time from bedtime until the start of sleep) calculated using actigraphy. Data for this outcome will be taken from the actigraph. Lights out/ snuggle down time** will be recorded by parents in the sleep diary. The start of sleep is defined using the actigraph as outlined in section 8.3.2. Sleep onset latency is calculated as the number of minutes between lights out/ snuggle down time and sleep onset.

9.4 Sample Size

Sample size calculations were undertaken using NQuery Advisor software version 4.0.

For the outcome 'total night-time sleep', the change between the total amount of sleep before randomisation and following randomisation will be calculated for each child. The titration period will not be used for the analysis of change. The null hypothesis is that there is no difference in the change over baseline in the total amount of sleep between the melatonin and placebo groups. The alternative hypothesis is that there is a difference in the change over baseline in the total amount of sleep. The study will be designed to detect a difference of one hour total sleep time in this change over baseline between the melatonin group and the placebo group. Assuming a common standard deviation of 1.7 (based on published data in similar populations/settings^(3;13)), a sample size of 47 per group, increasing to 57 per group to allow for estimated 20% loss to follow-up, will be required to provide 80% power using a t-test with a 0.05 two-sided significance level.

In the sample size calculation the difference to detect was deemed to be the minimum that would be beneficial to the child and their families. This was based on discussion with clinicians actively involved in the treatment of such children and discussion with affected families.

Table 4: Planned recruitment targets at each centre are:

Recruiting Centres	Target Accrual per centre	Recruiting Centres	Target Accrual per centre
Alder Hey Hospital	15	Derbyshire Children's Hospital	5
Royal Manchester Children's Hospital	10	Queens Medical Centre	5
Evelina Children's Hospital	17	John Radcliffe Hospital	14
University College Hospital London	12	Chesterfield Royal Hospital	8
Royal Devon and Exeter Hospital	6	Torbay Hospital	3

Birmingham Children's Hospital and Gulson Hospital	15	Bristol Royal Hospital for Children and Southmead Hospital	7
Queen Mary's Hospital	5	Victoria Blackpool Hospital	5
Arrowe Park Hospital	7	Leicester General Hospital	6
Southampton General Hospital	12	Sheffield Children's Hospital	6
University Hospital of Wales	8	Northampton General Hospital (this centre was never initiated and IMP was re-distributed to other centres)	0

N.B. Northampton was never initiated as a centre. Although centre targets remained unchanged, the packs of IMP allocated to Northampton were re-distributed between Manchester, Blackpool and UCLH to enable continued recruitment.

The final follow up should be completed 12 weeks after randomisation of the last participant and statistical analysis will begin immediately after this time point following the closure of the database for data entry.

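### The primary comparison is described as a change score with a t-test as its planning basis; the protocol should say that the analysis adjusts for baseline sleep and accounts for centre, or confirm that the SAP does

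*Protocol*

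**What the plan says.** Section 9.4 (Sample Size) defines the primary quantity: "the change between the total amount of sleep before randomisation and following randomisation will be calculated for each child". Both hypotheses are stated on it, the null as "The null hypothesis is that there is no difference in the change over baseline in the total amount of sleep" between the two arms. The target is to "detect a difference of one hour total sleep time in this change over baseline", with the variability given as "Assuming a common standard deviation of 1.7" and 47 evaluable children per group "to provide 80% power using a t-test with a 0.05 two-sided significance level". That is the only test named for the primary outcome.

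Section 9.3.1 fixes the two weeks: "Week T-1W will be used as the baseline to be compared with week T+11W". Section 9.2 gives the design constraint: "Randomisation will be stratified by centre"; section 7.1 says the same.

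Section 9.6 (Analysis Plan) adds CONSORT reporting, intention to treat, and a complete case analysis checked by imputation sensitivity analyses. Sections 9.1 and 9.6 leave the detail to a separate SAP, which is not among the documents at hand. No section of the protocol mentions adjustment for baseline sleep or for centre.

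**The concern.** A raw change score subtracts the whole baseline value, which amounts to setting the slope of follow-up on baseline to 1. If the true slope is different, part of the baseline variation stays in the outcome as noise, and a chance difference between arms at T-1W carries through to the estimate. Estimating the slope removes both problems with data the trial already collects.

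A slope below 1 is plausible here. Section 5.1 selects children for impaired sleep, and section 6.2 reviews severity again at T0W, directly after the baseline week. Some regression to the mean is therefore likely.

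The planning margin is also thin. The 57 per group with 20% loss leaves 57 × 0.8 = 45.6 evaluable, where the t-test has 78.8% power (45 per arm) to 79.7% (46 per arm).

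**Working it through.** **Inputs from the protocol.** Difference 1 h, SD 1.7 h, two-sided alpha 0.05, 47 evaluable per group (section 9.4); equal allocation (section 7.1).

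**Inputs not in the protocol, assumed here.** The correlation rho between T-1W and T+11W sleep, range 0.3 to 0.8; equal variances at the two weeks; 1.7 h as the SD of change. Section 9.4 calls 1.7 only a common SD and does not say whether it belongs to the change or to a single week.

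**1. The protocol's own figure.** Standard error = 1.7 × √(2/47) = 0.351 h, so the noncentrality is 1/0.351 = 2.85 on 92 df. Noncentral-t power is 80.6% at 47 per group and 79.7% at 46. The stated 47 is reproduced.

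**2. What baseline adjustment does to the variance.** Let s0 and s1 be the SDs at baseline and follow-up.

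- Change score: s0² + s1² − 2·rho·s0·s1
- Baseline-adjusted: s1²(1 − rho²)
- Difference: (s0 − rho·s1)²

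The difference is never negative, and it is zero only when the slope rho·s1/s0 equals 1. So in large samples adjustment is never less precise. With s0 = s1, the ratio of adjusted to change-score variance is (1 − rho²)/(2(1 − rho)) = (1 + rho)/2.

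**3. Power at 47 per arm, with 1.7 h as the SD of change.** The SD becomes 1.7 × √((1 + rho)/2).

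| rho (assumed) | variance ratio | SD (h) | power | n per group for 80% |
|---|---|---|---|---|
| change score | 1 | 1.700 | 80.6% | 47 |
| 0.3 | 0.65 | 1.371 | 93.8% | 31 |
| 0.5 | 0.75 | 1.472 | 90.3% | 36 |
| 0.7 | 0.85 | 1.567 | 86.4% | 40 |
| 0.8 | 0.90 | 1.613 | 84.5% | 42 |

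The standard error falls by 19% at rho 0.3 and by 5% at rho 0.8. At 45 per arm, close to what the planned loss leaves, adjusted power is 92.8%, 89.0%, 84.9% and 82.9% in the same order.

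**4. If 1.7 h is a single-week SD instead.** The SD of change is 1.7 × √(2(1 − rho)) and the adjusted SD is 1.7 × √(1 − rho²). At rho 0.3 these are 2.011 and 1.622, giving 66% and 84% power. At rho 0.5 they are 1.700 and 1.472, giving 81% and 90%. The variance ratio is unchanged.

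**5. Unequal variances.** Suppose the baseline SD is 0.7 of the follow-up SD (s0 = 0.7, s1 = 1), as selection on short sleep might produce.

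- rho 0.7: change 0.49 + 1 − 0.98 = 0.51; adjusted 1 − 0.49 = 0.51. The slope is 1 and there is no gain.
- rho 0.5: change 0.49 + 1 − 0.70 = 0.79; adjusted 0.75. The ratio is 0.95, not 0.75.

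**6. Centre.** Table 4 has 20 entries, one with target 0, so 19 are active and a fixed effect costs 18 df. Centre adjustment alone at 47 per arm gives 80.4%, 82.3% or 84.3% power if centre explains 0%, 5% or 10% of the variance (assumed shares). The effect lies between a trivial loss and a gain of about 4 points.

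**The case against.** A reader might infer that the protocol fixes an unadjusted t-test as the primary analysis and so discards precision. The text does not support that. The t-test appears once, under Sample Size, as the basis of the power calculation. No sentence says that the primary analysis will be a t-test or will be unadjusted, and sections 9.1 and 9.6 defer the detail to an SAP that may already adjust. The stated null is also compatible with adjustment: once T-1W sleep is a covariate, the treatment coefficient is the same whether the response is the change or the T+11W value.

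A reader might also infer bias from regression to the mean. Randomisation rules that out, because both arms are affected alike in expectation. What is left is chance imbalance and lost precision. Ignoring the centre strata is likewise generally conservative, not invalid.

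Finally, the size of the gain rests on inputs the protocol does not give, and step 5 shows that it can be zero.

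All of this stands, and it limits the point. It does not remove it. Section 9.4 does more than supply a sizing formula: it says the change will be computed per child, excludes the titration period from the analysis of that change, and states both hypotheses on it. An SAP written to match that section would naturally inherit the raw change score.

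**Conclusion.** The point holds in limited form. The comparison section 9.4 describes is valid and its 47 per group is correctly calculated. As described, though, it omits a baseline value already collected and a factor used in the randomisation. Baseline adjustment is in large samples never less precise than the raw change score, and it is more precise unless the slope is 1.

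Under equal variances and 1.7 h as the SD of change, the gain at 47 per arm is about 4 to 13 percentage points of power for an assumed rho of 0.8 down to 0.3. It shrinks towards nothing if the slope is near 1. The centre part is a matter of consistency with the stratified design and is worth roughly 0 to 4 points. Whether any precision will actually be lost depends on the SAP and cannot be settled from the protocol.

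**What to change.** State in sections 9.4 and 9.6 that the primary treatment effect is the treatment coefficient from a linear model for mean total night-time sleep in week T+11W (or, equivalently, for the change), with mean sleep in week T-1W as covariate and an allowance for centre. A random intercept is one option, since Table 4 has 19 active entries with targets of 3 to 17 children. Say that the t-test calculation is a conservative planning figure only, and report the raw change descriptively. If the SAP already specifies such a model, a sentence in the protocol pointing to it is enough.

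The cost is one or two sentences in the protocol and a matching line in the SAP. It needs no new data, no change of estimand and no change to the sample size.

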1 PROTOCOL SUMMARY

- Title:** The use of Melatonin in children with Neuro-developmental Disorders and impaired Sleep; a randomised, double-blind, placebo-controlled, parallel study.
- Phase:** II
- Population:** 114 children aged 3 years to 15 years 9 months, at randomisation, with a diagnosis of a neuro-developmental disorder in conjunction with a minimum six month history of impaired sleep as defined by not falling asleep within one hour of 'lights off' or 'snuggling down to sleep' at age-appropriate times for the child in 3 nights out of 5, and/or less than 6 hours of continuous sleep in 3 nights out of 5.
- Number of Sites:** Twenty five sites throughout England; see Appendix A for full details.
- Study Duration:** Potential participants will be screened and initially registered on study at T-4 Weeks. The family will be given a standardised booklet on basic sleep hygiene but no other intervention (behavioural, pharmacological or homeopathic) to try and improve their child's sleep. Sleep diaries and an actigraph will be provided with instructions for use and will be used for the duration of the 4 week sleep hygiene intervention. Contact will be re-initiated at T-2 weeks to check the sleep diaries and the actigraphy data and to stress the importance of a consistent bedtime. At the end of 4 weeks (T0), assuming the child continues to fulfil the entry criteria and further consent is provided; the child will be randomised into the study. Each child will be followed up for 12 weeks from date of randomisation, by a combination of home visits, telephone contact and clinic attendance.
- Description of Intervention:** The active compound (melatonin) and placebo (matching in package and appearance) will be administered 45 minutes prior to the child's usual bedtime; wherever possible, this time will remain the same throughout the study. The starting dose will be 0.5 mg and will increase every 7 days through 2mg and 6 mg up to a maximum of 12 mg, depending upon the patient's response to the preceding dose. The study treatment will be administered orally or, if the patient is not able to feed orally, through a nasogastric feeding tube or gastrostomy feeding tube; in these latter two situations the capsule will be opened and the study treatment suspended in an appropriate vehicle for administration.

Primary Outcome:

Total night-time sleep calculated using sleep diaries

[figure not shown]
Secondary Outcomes:

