7 TRIAL TREATMENT/S

7.1 Introduction

This study is designed as a randomised, controlled, double-blind, multicentre clinical trial comparing the effects of melatonin versus placebo in children with neuro-developmental disorders and impaired sleep. Patients will be treated for a period of 12 weeks and will be followed up throughout this 12 week period.

Patient assessment will be stopped when all patients reach 12 weeks of treatment and/or follow-up.

Patients will be stratified by centre and randomised equally between the two groups:

1. Melatonin
2. Placebo

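### Section 9.4: 57 per group with 20% loss leaves 45.6 evaluable and about 79.3% power, not the stated 47 and 80%

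*Protocol*

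**What the plan says.** Protocol section 9.4 bases the sample size on the change from baseline in total night-time sleep, compared between melatonin and placebo. The target is given as follows: "The study will be designed to detect a difference of one hour total sleep time in this change over baseline". The variability is "Assuming a common standard deviation of 1.7", in hours by implication, since the difference is in hours. The result is "a sample size of 47 per group, increasing to 57 per group to allow for estimated 20% loss to follow-up", which "will be required to provide 80% power using a t-test with a 0.05 two-sided significance level". Section 7.1 gives equal allocation. The Protocol Summary carries the doubled figure: "114 children aged 3 years to 15 years 9 months, at randomisation".

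The formula for the loss allowance is not given. Section 9.5 provides a blinded check of the SD after 30 children, with a route to more recruitment if the SD is larger than assumed. It also says that missing data will be monitored, but it sets no rule for revising the target if the loss rate differs from 20%.

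**The concern.** A loss allowance should leave the required number after the loss has occurred, so the required number is divided by the retained fraction. Multiplying by one plus the loss rate gives too few. The step from 47 to 57 looks like the multiplication. If so, the stated loss rate, number randomised, number evaluable and power cannot all hold together.

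What is at stake is the accuracy of a published design statement. Section 9.6 commits the trial to CONSORT reporting, so the sentence is likely to be reproduced in the report, where a reader can check it by hand. Neither the design nor the analysis depends on it.

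**Working it through.** **Inputs** (section 9.4, with allocation from section 7.1): difference 1 hour; SD 1.7; two-sided alpha 0.05; power 80%; two-sample t-test; 1:1 allocation; 20% loss; 57 per group randomised.

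**1. The plan's base figure.** The normal approximation gives n = 2 x (1.960 + 0.842)² x 1.7² / 1² = 45.4, so 46 per group. The exact noncentral t solution is 46.35, so 47 per group, with power 80.6%. The stated 47 is reproduced.

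**2. The step from 47 to 57.**
- Multiplying: 47 x 1.2 = 56.4, rounded up to 57. This matches the printed figure.
- Dividing: 47 / 0.8 = 58.75, rounded up to 59.

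**3. What 57 delivers at 20% loss.** 57 x 0.8 = 45.6 per group. In total, 114 x 0.8 = 91.2 against 2 x 47 = 94.

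| Evaluable per group | Exact t-test power |
|---|---|
| 47 | 80.6% |
| 46 | 79.7% |
| 45.6 | 79.3% |
| 45 | 78.8% |

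Letting the number retained vary binomially in each group (57 children, each retained with probability 0.8) gives an average power of about 79.2%, so working with the expected number does not mislead.

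**4. The loss that 57 can absorb.**
- To keep 47 evaluable: 1 - 47/57 = 17.5%.
- To keep 80% power: 1 - 46.35/57 = 18.7%.

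**5. The number needed if 20% stands.**
- To keep 80% power: 46.35 / 0.8 = 57.93, so 58 per group (116 in total).
- To keep 47 evaluable: 58.75, so 59 per group (118 in total).

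The printed 57 is below both, so rounding does not rescue it.

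**The case against.** The strongest reply is that the gap is too small to matter. At 45.6 per group the shortfall from 80% is about 0.7 points, less than the rounding of the SD can produce: with 45.6 per group, power is 81.7% if the SD is 1.65 and 77.0% if it is 1.75, and an SD of 1.686 restores 80%. The SD is the larger uncertainty, and section 9.5 provides for checking it. The 20% is itself described as an estimate. All of this stands as a statement of size. It does not make the printed figures agree, because they are stated for an SD of 1.7 and a loss of 20%, and the SD check does not revisit the loss rate.

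Three stronger readings are tempting, and the document does not support them.

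- **The trial is four children short (114 against 118).** The figure 118 protects 47 evaluable per group. Protecting 80% power takes only 116. More importantly, no practical shortfall is shown: the centre targets in Table 4 of the same section sum to 166, and the protocol does not explain how they relate to 114.
- **The sponsor multiplied by 1.2.** That fits the numbers exactly, but it is an inference. The mismatch does not depend on it, since 57 with 20% loss does not leave 47 however 57 was reached.
- **The rule requiring 5 of 7 diary nights leaves the design with no slack.** Section 9.3.1 does apply that rule to the primary outcome, and a child still in follow-up could fail it at week T+11W. However, diary completion is an entry condition at T0W (sections 5.1 and 6.2), which screens out much of the baseline problem. Section 9.5 plans to limit missing data, and section 9.6 plans imputation sensitivity analyses. The protocol gives no rate for such exclusions. As an illustration only, an assumed 25% non-evaluable in all would leave 42.75 per group and 76.7% power.

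**Conclusion.** The point holds as a minor arithmetic inconsistency. With the protocol's own inputs, 57 randomised per group and 20% loss give 45.6 evaluable per group and about 79.3% power. Section 9.4 therefore overstates the evaluable number by 1.4 per group and the power by about 0.7 percentage points. The direction is unfavourable, and no other part of the protocol corrects it.

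The result assumes the stated SD of 1.7, equal loss in the two arms and an unadjusted t-test, all as section 9.4 implies. A reader might infer an underpowered trial or a recruitment target that must rise; neither follows from these figures.

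**What to change.** Restate the one sentence in section 9.4 and leave recruitment as it is. Either wording is accurate:

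- 57 per group with 20% loss to follow-up gives about 79% power; or
- 57 per group retains 47 evaluable with up to 17.5% loss, and 80% power is kept up to about 18.7% loss.

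The 17.5% and 18.7% should not be merged, since they answer different questions. If the sponsor would rather keep 20% loss as a stated assumption together with one of the other figures, section 9.4 and the Protocol Summary should give 58 per group (116) for 80% power, or 59 per group (118) for 47 evaluable. The method of inflation should be named in the same sentence.

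The cost is one sentence and a slightly less favourable stated figure. Choosing 116 or 118 instead would add two or four children to the stated target. A short note on how the Table 4 centre targets, which sum to 166, relate to 114 would remove a separate ambiguity.
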